5.2. Exclusion Criteria

- The participant may not enter the study if they have any contraindication to magnetic resonance imaging (standard MR exclusion criteria including pregnancy, extensive tattoos, pacemaker, shrapnel injury, severe claustrophobia).
- Patients with known autoimmune hepatitis, viral hepatitis, Wilson's disease, haemoglobinopathies or significant structural renal tract abnormality.
- Patients with known excessive alcohol intake.
- Any other cause, including a significant disease or disorder which, in the opinion of the investigator, may either put the participant at risk because of participation in the study, or may influence the participant's ability to participate in the study.

6. Sample size

The primary endpoint of the study is to compare the MRI metrics for liver fibroinflammation in those patients with type 2 diabetes at baseline vs. individuals who are healthy and non-diabetic. Values for the healthy, non-diabetics will be provided from data from the UK Biobank (UKBB)(30) or from other studies (31). Healthy individuals will be matched to the diabetic population based on gender, age and ethnicity. Analysis will be based on a two-sample, two-sided t-test.

The sample size required to perform a t-test with 90% power and alpha of 0.05 would require n=150. Based on MRI metric for liver fibroinflammation (cT1) this assumes:

- Detection of a 24.87 ms difference in cT1 in liver (This represents 50% of the difference in cT1 between self-reported diabetes vs healthy subgroups within the UK Biobank), based on unpublished data from Perspectum)
- SD of 42ms (pooled SD from self-reported diabetes and healthy subgroups within UKBB, based on unpublished data from Perspectum)
- 20% drop-out rate.

Secondary endpoints of the study include separate comparisons of MRI metrics for liver fat infiltration and volume in patients with type 2 diabetes vs. the same metrics in healthy, non-diabetic individuals. Values for the healthy, non-

diabetics will be provided from data from the UK Biobank (30) or or from other studies (31) and will be selected based on the matching of gender, age, ethnicity to the patients from this study with type 2 diabetes. Analysis will be based on two-sample, two-sided t-tests.

Based on MRI metric for liver fat infiltration (PDFF), the sample size required to perform the t-test with 90% power and alpha of 0.05 would require n=150. This assumes:

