- Detection of a 2.4% difference in PDFF [This represents 63% of the difference in PDFF between self-reported diabetes vs healthy subgroups within UK Biobank, unpublished Perspectum]
- Measurement SD of 5.4% (Pooled SD from self-reported diabetes and healthy subgroups within UK Biobank, based on unpublished data from Perspectum)
- 20% drop-out rate.

Based on MRI metric for liver volume, the sample size required to perform the t-test with 90% power and alpha of 0.05 would require n=150. This assumes:

- Detection of a 0.084 L difference in liver volume in liver (This represents 6% of the pooled mean from UK Biobank data, unpublished Perspectum)
- Measurement SD of 0.289 L (pooled mean from UK Biobank data, unpublished Perspectum)
- 20% drop-out rate.

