10.2. Analysis plan

Descriptive statistics will be used to summarise subject characteristics. Summary data will be calculated for MRI metric values (Table 3). Normality will be determined by use of the Shapiro-Wilk test. Results will be expressed as means with standard deviation (SD) for continuous variables and as numbers and percentages for categorical variables.

Analysis of variance will be used to test for differences between multiple groups.

The primary endpoint will be a comparison of MRI metric values for fibro-inflammation in the liver compared to a matched non-diabetic control group from the UK Biobank(30) or from other studies (31) (Table 3). This will be assessed with a two-sample, two-sided t-test. Secondary endpoints include a comparison of individual MRI metric values [summarised in table 3 below] in individual organ associated with T2D and its comorbidities [summarised in table 3 below] at baseline (visit 1/visit 2) compared to a matched non-diabetic control group from the UK Biobank or other studies. These will also be assessed with two sample, two-sided t-tests. Additionally, the prevalence of mean liver PDFF and / or mean liver cT1 above NAFLD thresholds in the study cohort will be compared to the matched non-diabetic control group, using a Chi-squared test.

MRI metric	Organ(s) or Location(s)	Associated organ characteristic
For primary endpoint		
cT1	Liver	Fibro-Inflammation
For secondary endpoints		
Diameter of Aorta	Heart	Local Blood Flow
Aortic Distensibility	Heart	Elasticity of Aorta
T1	Spleen, Kidney, Pancreas	Fibro-Inflammation
T2*	Spleen	Iron Level
PDFF	Liver, Spleen, Pancreas	Fat content
Volume	Liver, Spleen, Kidney, Pancreas	Size
Optional exploratory endpoint metrics		
T2* Gradient	Kidney	Oxygenation
D	Kidney	Glomerular Filtration
PDFF	Kidney	Fat Content

Volume of Visceral Adipose Tissue (VAT)	Abdomen	Fat Content
Abdominal Subcutaneous Adipose Tissue Volume (ASAT)	Abdomen	Fat Content
Skeletal Muscle Index	Abdomen	Muscle Content

Table 3 - MRI metrics in relevant organs

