Change from baseline in MRI metrics values at 6 to 9-months post-treatment will be assessed as secondary endpoints in each organ. These will be assessed with linear mixed effects model with an interaction variable of time. The change from baseline in proportion of patients at 6 to 9 months with mean PDFF and / or mean cT1 above NAFLD thresholds, across the whole study cohort, will be assessed using Chi-squared tests. Equivalent changes from baseline at 6 to 9 months will be assessed for HbA1c (glycaemic control), and other circulating biomarkers utilised in the clinical pathway for T2D, NASH and CKD [serum creatinine and eGFR (kidney), urine albumin creatinine ratio (kidney), lipids (NALFD), LFT (liver)], using linear mixed effects to assess changes over time. Odds ratios will be calculated by logistic regression analysis in relation to cardiovascular, liver, pancreatic and kidney-related events and or death, including hospital admissions, at 1, 3 and 5 years from baseline.

Exploratory endpoints will investigate the potential influence of glycaemic control/weight and of glucose/lowering therapies (oral/injectable agents) on prevalence of abnormality based on thresholds set from the healthy controls and on rate of progression for both biochemical and MRI-metrics, in subgroup analyses (including subgroups with abnormalities in multiple organs). Multiple testing will be corrected with Bonferroni correction. In addition, analysis of covariance will provide estimates of MRI metrics, adjusting for potential confounders such as baseline MRI metric, type of co-morbidity, type of therapeutic, HbA1c values, anthropometric measures and organ-specific circulating biomarker values as covariates. Similarly, additional associations of MRI metrics to biomarkers that are optional [for example left ventricular strain from the ECHO] or not in standard of care [for example pancreatic lipase] may be analysed, if evaluated locally or from stored, consented additional blood samples. Thresholds will be set based on Kaplan–Meier analysis to establish the proportions of patients in different MRI metric categories that remain free of diabetes-related events in the follow-up period. Differences between the curves will be compared using the log-rank test.

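### Bonferroni is fixed for the exploratory and subgroup analyses, although Holm's procedure gives the same family-wise guarantee and is never less powerful

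*Protocol*

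**What the plan says.** Section 10.2 (Analysis plan) takes the endpoints in order. The primary comparison of liver cT1 is one two-sample t-test. For the secondary baseline comparisons of the other MRI metrics it says "These will also be assessed with two sample, two-sided t-tests". Changes at 6 to 9 months and the odds ratios follow. None of these carries a multiplicity correction.

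A new paragraph then begins: "Exploratory endpoints will investigate the potential influence of glycaemic control/weight and of glucose/lowering therapies (oral/injectable agents) on prevalence of abnormality". Its first sentence ends with the subgroup analyses, and the next sentence is the protocol's only multiplicity rule: "Multiple testing will be corrected with Bonferroni correction". It gives neither the family nor the number of tests. The paragraph goes on to covariance analysis, optional biomarker associations and log-rank comparisons. The closing paragraph of 10.2 promises effect sizes with 95% confidence intervals and mentions no adjustment of them.

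Section 6 (Sample size) powers two secondary endpoints, liver fat and liver volume. For each it says that "the sample size required to perform the t-test with 90% power and alpha of 0.05 would require n=150".

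**The concern.** Where a protocol commits to a specific correction, that correction should not be one that another procedure improves on under the same assumptions. Bonferroni compares every p-value with 0.05/m. Holm compares only the smallest with 0.05/m and relaxes the limit after each rejection. Both guarantee a family-wise error rate of at most 0.05 whatever the correlation between tests, so Bonferroni's extra strictness buys no stronger guarantee.

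The stake is modest: some real subgroup or therapy associations would be missed that Holm would have found. The loss grows with the number of real effects. That matters somewhat here because the exploratory analyses span many related MRI and biochemical metrics, several of which could move together.

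**Working it through.** **Is there a plan figure to reproduce?** No. The protocol attaches no family size, effect size or power to the Bonferroni rule. The check is therefore a general argument plus an illustration.

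**Why Holm rejects at least as much.** Order the p-values from smallest to largest. Holm compares the j-th with 0.05/(m − j + 1) and stops at the first failure. Every limit is at least 0.05/m, so any p-value at or below 0.05/m, together with all smaller ones, passes. Everything that Bonferroni rejects, Holm rejects.

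**Why the error guarantee is the same.** Let m0 hypotheses be truly null. Before the first false rejection, Holm can have rejected at most m − m0 hypotheses, so the limit at that step is at most 0.05/m0. The chance that any of the m0 null p-values falls below that is at most m0 × 0.05/m0 = 0.05. This uses no independence.

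**Concrete limits with m = 13.** Bonferroni: 0.05/13 = 0.00385 throughout. Holm: 0.05/13 = 0.00385, then 0.05/12 = 0.00417, down to 0.05/7 = 0.00714 at the seventh step and 0.05 at the last. If the two smallest p-values are 0.001 and 0.004, Bonferroni rejects one hypothesis and Holm at least two.

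**Size of the gain.** Assumptions: m = 13, borrowed as a stand-in from the secondary metric-organ pairs in Table 3 (aortic diameter 1, distensibility 1, T1 3, T2* 1, PDFF 3, volume 4). Each real effect has 90% power at an unadjusted two-sided 0.05, which means an expected z of 1.960 + 1.282 = 3.242. Bonferroni power is then Φ(3.242 − 2.890) = Φ(0.352), about 64%. Simulation with 200,000 runs gives the following power per real effect:

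| Real effects of 13 | Bonferroni | Holm, independent tests | Holm, correlation 0.5 |
|---|---|---|---|
| 3 | 63.7% | 65.0% | 64.8% |
| 7 | 63.6–63.7% | 68.2% | 67.6% |
| 13 | 63.8% | 78.7% | 75.8% |

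The gain with independent tests runs from 65.0 − 63.7 = 1.3 points to 78.7 − 63.8 = 14.9 points. In a separate check with one real effect of standardised size 0.444 and 120 per group, both procedures gave 71%.

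**Hand check with m = 2, both effects real, independent tests.** Bonferroni power is Φ(3.242 − 2.241) = 0.841. Holm adds the cases where this p-value lies between 0.025 and 0.05 and the other is below 0.025: 0.841 + (0.900 − 0.841) × 0.841 = 0.891. The simulation gave 84.2% and 89.1%.

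**Simulated family-wise error, m = 13, independent tests (Bonferroni, Holm).** No real effects: 4.9%, 4.9%. Three real: 3.8%, 4.5%. Seven real: 2.3%, 3.7%. Holm uses more of the allowance but stays within 5%.

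**The case against.** Four points can be made on the other side.

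- **Bonferroni is valid.** This stands. Choosing it is conservative, and its realised error rate is lower than Holm's when some effects are real. The guarantee that can be claimed in advance is nevertheless the same.
- **Bonferroni has directly matching simultaneous intervals, and section 10.2 reports confidence intervals.** This is the one real trade-off. It carries limited weight because the protocol promises 95% intervals without any adjustment and so, as written, does not use that advantage.
- **The gain may be negligible.** This stands when few effects are real. The larger gains depend on many being real, which the protocol does not claim.
- **The family and the test count can be left to the statistical analysis plan.** This stands too, and their absence is not the point. The method is already fixed in the protocol, so the choice of method can be judged here.

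A reader might infer something stronger: that the Bonferroni sentence contradicts the secondary power stated at 0.05. If it did reach 13 secondary tests, power with an assumed 120 per group (150 less 20%, 1:1 matching) would fall from 93% to about 71% for liver fat and from 61% to 26% for liver volume. The text does not require that reading. The secondary tests are set out earlier and without correction, Section 6 powers two of them at 0.05, and the Bonferroni sentence belongs to the exploratory paragraph. Holm would not remove such a conflict either, since its first step also uses 0.05/m.

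Nor is it an error in itself that secondary tests run uncorrected. Thirteen independent null tests at 0.05 would give at least one false positive with probability 1 − 0.95^13 = 0.487, but the protocol has a single primary endpoint and makes no family-wise claim for the secondary ones.

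**Conclusion.** The point holds as a low-priority improvement in method. For the exploratory and subgroup analyses, Holm's procedure offers the same family-wise guarantee as Bonferroni and at least its power. In the illustrations the gain runs from about 0 to 15 percentage points per real effect, according to how many effects are real. Family size, effect sizes and correlations are assumptions, because the protocol gives none; the ordering of the two procedures does not depend on them.

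The documents do not contradict the secondary alpha of 0.05. The liver-volume power of about 61% at an uncorrected 0.05, with an assumed 120 per group, is a separate sample-size matter. It follows from 0.084/0.289 = 0.291 standard deviations: 0.291 × √(120/2) = 2.25, and Φ(2.25 − 1.96) = 0.61. It is no evidence for or against the choice of correction.

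**What to change.** In section 10.2, replace the Bonferroni sentence with one along these lines: *In the exploratory and subgroup analyses, multiple testing will be handled with Holm's procedure at a family-wise 0.05; secondary endpoints are tested at an unadjusted two-sided 0.05.* The second half states what sections 6 and 10.2 already imply. The list of tests in each family can go in the statistical analysis plan, fixed before the data are analysed.

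The cost is one sentence, with no new data and no change to the sample size. The downside is that Holm has no simple matching simultaneous intervals. The 95% intervals would be reported and labelled as unadjusted, so an interval may exclude no effect where the Holm-adjusted test does not reject.

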Metformin is typically the initially treatment for T2D (8). However, due to its progressive nature, metformin monotherapy proves to be inadequate in maintaining long-term glycaemic control (9). Metformin has been used safely and effectively for decades, but newer drugs are becoming available. Numerous recent studies have shown that newer drug classes, including the SGLT-2 inhibitors and GLP1 receptor agonists (GLP-1RA), have substantial beneficial effects

beyond modulation of glycaemic levels, and can confer protection against CVD and CKD (10–13). It is now recommended that use of these drugs is advocated for high risk populations with evidence of CKD or CVD (14–16).

This study aims to develop an MRI-based method that is able to identify the individuals at high risk of disease complications, looking particularly at renal, hepatic and cardiovascular pathology, and further compare this to the conventional biochemical approach. This has future potential in assisting in the stratification of patients to the most appropriate tailored treatment for their disease. We will further evaluate the additional synergistic value of incorporating MRI-metrics into patient pathways.

There is a healthcare need to provide further decision-making support for clinicians in the care of patients at risk or diagnosed with T2D. This would combine multi-modality approaches, an incorporation of biochemical evaluation and imaging techniques. There is also a pressing need for treatment stratification to identify the T2D patients who would benefit from being triaged to receive the newer, more expensive drugs. This would also empower patients and aid in their engagement of the lifestyle changes often required for treatment. This should have the added benefit of reducing associated NHS costs by minimising the pool of patients with severe disease, who would be highlighted through early detection and early medical management.

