To address this growing need, we propose adding a complementary imaging aspect to the currently used biomarkers. MRI, specifically, provides excellent soft-tissue contrast. Perspectum’s LiverMultiScan™ is a quantitative multiparametric MRI method, FDA-cleared and CE-marked, that is used to detect and stage early liver disease. It is already widely used in pharmaceutical trials for NAFLD therapeutics. The MRI metrics from LiverMultiScan™ can quantify changes to liver tissue characteristics, like fibro-inflammation and fat, as a result of intervention (for example, bariatric surgery - see Fig. 1). The accuracy and reproducibility of LiverMultiScan™ has been demonstrated in studies scanning patients within different MRI scanners. It continues to be further supported by data from clinical trials in liver disease cohorts, from comparative studies that include healthy controls, as well as whole-population studies in the UK and US (17–24).

[figure not shown]

Figure 1 - Example of MRI metrics and images from LiverMultiScan™ before and after bariatric surgery

With this study we aim to develop a new MRI image analysis technique, “ATLAS”, that builds on LiverMultiScan™ technology. We also plan to gather clinical evidence that will demonstrate the potential added value to the NHS, as well as support future regulatory clearance. The phenotypical information that ATLAS delivers, combined with information from circulating biomarkers, will form the basis of a future clinical decision support tool for T2D (Fig. 2).

[figure not shown]

Figure 2 – An example schematic of the impact of ATLAS in the clinical pathway of T2D, based on MRI metrics of liver and cardiovascular system health

Perspectum has pilot data showing that LiverMultiScan can:

- estimate portal hypertension (spleen),
- detect pancreatitis,
- characterise the tissue of the kidneys

This study looks at the potential to extend LiverMultiScan to each of the other relevant organs – pancreas, kidneys and spleen. The technical development of “ATLAS” will be complemented by the accumulation and analysis of clinical data, circulating biomarkers and imaging. This information will be obtained from three diverse UK clinical centres (Liverpool, Oxford and London).

The innovation comes from combining a number of quantitative MRI metrics to achieve this (Fig. 3):

- volumes - for liver, spleen, kidneys, pancreas (25–27);
- fibroinflammation: cT1 and/or T1 – for liver, spleen, kidneys, pancreas (25);

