The results will be expressed as effect sizes and 95% confidence intervals (95% CI). Spearman and/or Pearson’s correlations will be calculated to test associations between categorical and / or continuous variables, for example significant correlations between MRI metrics and weight, and between MRI metrics and biochemical metrics. To determine the diagnostic utility of MRI in these cohorts for assessing organ dysfunction, receiver-operating characteristic analyses will be carried out.

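### Section 10.2 lets follow-up events set the MRI thresholds, then tests and measures the separation of the resulting groups on the same events

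*Protocol*

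**What the plan says.** Protocol Section 10.2 describes the time-to-event analysis within its exploratory paragraph: "Thresholds will be set based on Kaplan–Meier analysis to establish the proportions of patients in different MRI metric categories". The outcome is freedom from diabetes-related events during follow-up. The next sentence reads "Differences between the curves will be compared using the log-rank test". No rule for choosing a cut and no set of candidate cuts is given. Selection-adjusted tests, resampling and validation data are not mentioned.

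Two other kinds of threshold appear in Section 10.2, for other purposes. The exploratory paragraph examines "prevalence of abnormality based on thresholds set from the healthy controls", and the Chi-squared comparisons use NAFLD thresholds for liver PDFF and cT1. Neither depends on follow-up events, and neither is named as the source of the Kaplan-Meier categories.

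The one safeguard is a general sentence earlier in the same paragraph, directly after the subgroup analyses: "Multiple testing will be corrected with Bonferroni correction". It does not say which tests are counted. Section 10.2 also asks for results as effect sizes with 95% confidence intervals, so the size of the separation will be reported as well as the p-value.

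**The concern.** A log-rank p-value is valid when the groups are fixed without looking at the outcome. Here the outcome appears to define the groups. Two errors follow if the cut is picked because it separates the curves well.

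1. The p-value is that of the best of several tests but is read as if it came from one.
2. The difference in event-free proportion at the chosen cut is too large on average, because the cut was chosen partly for the chance component of that difference. Bonferroni changes the p-value threshold and leaves the estimate as it was.

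A metric with no prognostic value could then show separated curves too often, and a real difference would look larger than it is. This bears on the aim in Section 2.1: "This study aims to develop an MRI-based method that is able to identify the individuals at high risk of disease complications". The same section says that ATLAS information, combined with circulating biomarkers, "will form the basis of a future clinical decision support tool for T2D". The protocol does not say that these particular cut-points will be used in that tool.

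**Working it through.** **Plan's own figure.** The protocol gives no number for the Kaplan-Meier analysis. Its sample size supplies the range of n. For cT1 (Section 6: difference 24.87 ms, SD 42 ms, two-sided alpha 0.05, power 90%), n per group = 2 × (1.96 + 1.2816)² × (42/24.87)² = 59.9, so 60. Two groups give 120, and 120/0.8 = 150. The stated 150 is reproduced as the total of two equal groups. With 150 patients enrolled and 20% drop-out, 120 remain, so I used n = 120 and n = 150.

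**Assumptions not in the documents.** One metric; exponential event times; 5-year event risk 15, 25 or 40%; administrative censoring at 5 years; 20% lost over 5 years; the cut with the largest |z| is chosen.

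**Calculation.** At each candidate cut, z = (O − E)/√V from the log-rank test. The largest |z| is kept and its p-value read as from a single test. For K independent cuts the error would be 1 − 0.95^K: 9.8% for K = 2 and 14.3% for K = 3. Neighbouring cuts are correlated, so the simulated rates are somewhat lower.

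**False-positive rate with no true association** (8,000 replicates per setting; range over settings). Table 3 lists 14 primary or secondary organ-metrics (1 + 2 + 3 + 1 + 3 + 4) and 6 optional ones, 20 in all, so Bonferroni over metrics alone gives 0.05/20 = 0.0025.

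| Cut rule | Candidate cuts K | p < 0.05 | p < 0.0025 (metrics counted, cuts not) | p < 0.05/K (every cut counted) |
|---|---|---|---|---|
| Pre-fixed median | 1 | 5.0-5.4% | 0.2-0.3% | as p < 0.05 |
| Best tertile cut | 2 | 8.9-9.6% | 0.4-0.6% | 4.2-5.0% |
| Best quartile cut | 3 | 12.4-13.0% | 0.7-1.0% | 4.3-4.8% |
| 25th-75th percentile search | 61-75 | 27.0-28.5% | 2.2-2.7% | 0.7-1.2% |
| 10th-90th percentile search | 97-121 | 40.1-43.6% | 5.3-5.5% | 1.6-2.2% |

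Bonferroni over metrics alone leaves the inflation in place: 0.25% is intended, and the best quartile cut gives 0.7-1.0%. Counting every cut controls the error, conservatively for fine searches.

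**Separation at 5 years, in percentage points of event-free proportion.** The right-hand columns assume a true hazard ratio of 1.2 or 1.4 per SD (4,000 replicates per setting).

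| Cut rule | No true association: median apparent difference | True difference at chosen cut | Mean overstatement |
|---|---|---|---|
| Pre-fixed median | 4.1-6.5 | – | −0.2 to 0.0 |
| Best quartile cut | 7.9-12.2 | 4.2-16.9 | 2.1-5.4 |
| 25th-75th search | 10.2-15.9 | 4.1-16.7 | 3.4-9.0 |
| 10th-90th search | 13.6-21.1 | 4.4-17.8 | 5.4-13.2 |

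Relative to the true difference, the overstatement is 28-54% for the best quartile cut and 49-88% for the 25th-75th search.

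**Check with other settings.** A separate simulation (2,000 replicates; risk 10, 20 or 40%) gave false-positive rates of 4.3-6.0% at a fixed median, 11.7-13.1% for 3 cuts, 29.9-31.9% for 17 and 37.1-42.8% for 81. Counting all cuts brought these down to 1.8-5.6%. On the hazard-ratio scale (n = 150, risk 20%, log hazard ratio 0.4 per SD), the mean estimate was 2.40 against a true 1.92 with 3 cuts (2.40/1.92 = 1.25) and 2.90 against 1.97 with 17 cuts (2.90/1.97 = 1.47). At the fixed median it was 1.87-1.89.

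**The case against.** The strongest reply is that the protocol names no search, no best-cut rule and no maximised statistic. Both errors depend on the cut being chosen for separation, and the choice of threshold could be left to an SAP. The sentence can also be read differently. Its stated purpose is to estimate event-free proportions within MRI categories, which fits categories formed beforehand. Even if a threshold is read off the curves, a log-rank test made first across fixed categories would keep a valid p-value. The Bonferroni sentence may be meant to cover candidate cuts. The analysis is exploratory, and the magnitudes rest on assumed event risks, hazard ratios and search ranges.

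Much of this stands as a limit on the claim. The size cannot be fixed from the documents, and on the reading with categories given beforehand neither error arises. It does not remove the point. The text says that the thresholds are set from Kaplan-Meier analysis, which is a stated procedure, and an SAP that followed it would inherit the problem. The Bonferroni sentence, even at its widest, leaves the estimate uncorrected. Exploratory status makes a loosely controlled p-value tolerable, but it does not make a biased effect size and its confidence interval correct.

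**Conclusion.** The concern holds, conditionally. On its plain reading, Section 10.2 defines MRI categories from the events on which they are then compared. If cuts are chosen for separation, a nominal 5% test has a false-positive rate per metric of about 9-10% with two candidate cuts, 12-13% with three, and 27-44% with a percentile search, unless every candidate cut is counted. The 5-year difference is overstated by about 2-5 points at the best quartile cut and 3-9 points in a 25th-75th percentile search, whatever is done to the p-value. These figures assume 120-150 patients, 15-40% event risk, 20% loss and, for the bias, a hazard ratio of 1.2-1.4 per SD.

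The scope is limited to this exploratory analysis. The primary t-test, the secondary comparisons and the logistic regression for secondary objective 6 are not affected. The wording should be changed, with moderate confidence, because the intended rule is not stated.

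**What to change.** Reword Section 10.2 so that the categories are fixed without reference to follow-up events. For example: *MRI metric categories will be defined by the NAFLD thresholds (liver cT1, PDFF) and, for other metrics, by healthy-control thresholds or prespecified quantiles; event-free proportions will be estimated by Kaplan-Meier and compared by log-rank test.* If categories given beforehand were always intended, this only makes that clear.

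If thresholds derived from outcome are wanted, keep them and add three things:

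- a p-value corrected for maximal selection, or Bonferroni with every candidate cut counted;
- a bootstrap or cross-validated estimate of the separation;
- a statement that the cut-points are hypothesis-generating until validated in separate data.

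The cost is wording in Section 10.2, with no new patients, visits or measurements; the second option adds some analysis work. There will be fewer nominally significant exploratory results. Under the first option the study will not identify the cut with the greatest difference in event risk.
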